6.0 Inclusion Criteria

- 6.1 All patients diagnosed with Covid-19 will be registered on the study regardless of their severity, but only those who meet high risk criteria will be treated with steroids. Those who do not meet the criteria will only be registered with no need to collect further data except baseline labs and CT chest. They should sign the consent form and the data manager can collect the rest of the information.
- 6.2 Male or female patients of 21 years or older diagnosed with Covid-19 by PCR or by rapid serological test will be eligible. Diagnosis of Covid-19 will be established by means of either the PCR molecular test or with the rapid serologic test or both. (see figure 3)

We have learned recently that some cases produce IgG very early and presence of IgG doesn't mean that infection is late. Those who are IgM positive but PCR negative, will be considered as "suspicious for Covid-19"; however, if their clinical presentation is typical for Covid-19, (see below) they will be counted as a positive diagnosis. Those who are IgM positive but PCR negative, for purposes of analysis will be divided as "polysymptomatic" (2 or more symptoms characteristic of Covid-19) or "not polysymptomatic". The symptoms considered as characteristic are fever, cough, dyspnea, myalgia, diarrhea, anosmia/dysgeusia, malaise, headache, abdominal pain, neurological symptoms (paresthesiae, delirium etc).

- 6.2 a. Patients who have negative Covid IgG and IgM but whose PCR results are not available yet and who have typical symptoms of Covid-19 (see section 6.2 above), or who have typical CT chest findings such as ground glass opacities, will be considered eligible. If PCR later on turns to be negative, the patient will be retrospectively considered as ineligible.
- 6.3 Eligible patients will be registered on study on or before 10 days from first onset of symptoms. Patients whose symptoms started > 10 days ago; but who are not in respiratory failure are eligible if they are still symptomatic.
- 6.4 In order to be treated with methylprednisolone, they must meet at least two of the following criteria on or shortly before day 10 (but not before day 7)

 from first onset of symptoms, in order to avoid treatment during viral phase; if two criteria are met before day 7, patient is eligible but treatment should not start before day 7 of illness:
 - 6.4.1 Serum IL-6 \geq 10 pg/ml before day 10.
 - 6.4.2 Ferritin> 500 ng/ml before day 10.
 - 6.4.3 D-dimer > 1 mg/L (1,000 ng/ml) before day 10.
 - 6.4.4 CRP > 10 mg/dL (100 mg/L) before day 10.
 - 6.4.5 LDH above normal before day 10.

- 6.4.6 Lymphopenia (absolute lymphocyte count <900) before day 10.
- 6.4.7 O₂ saturation <94% by pulse oximetry, but more than 91%, before day 10.
- 6.4.8 CT chest with evidence of infiltrate(s).
- 6.5 Interpretation of results of rapid and PCR molecular tests:
 - 6.5.1 Those with serological positive test but negative molecular PCR test will be analyzed based on the clinical context. See below.
 - 6.5.2 Those who present with at least 2 of the following typical symptoms of Covid-19 (cough, fever, dyspnea, diarrhea, anosmia) will be considered as likely cases of Covid-19 while those with one or less symptoms will be considered as unlikely cases but will still be considered evaluable. They will be analyzed separately.
 - 6.5.3 Those who are PCR positive and serology positive or negative will be considered as definitive cases.
- 6.6 The CALL score will be used in the analysis of all cases (11). This score represents a composite index based on presence of comorbidities, age >60, lymphopenia and elevated LDH. Those cases with a score >6 have greater than 50% risk for serious complications.
- 6.7 Simultaneous treatment will be allowed with the following drugs: remdesivir, hydroxychloroquine, azithromycin, vitamin C, doxycycline, colchicine, zinc and ivermectin. Patients who have received 1 single dose of dexamethasone or methylprednisolone will be eligible. **Their use is not considered as a basis for exclusion** from this trial.

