2.0 Schedule of Study Assessments

- 2.1 At, or prior to, entry into study:
 - 2.1.1 History and Physical exam
 - 2.1.2 Labs: CBC, CMP, LDH, arterial blood gases, serum IL-6, serum ferritin, CRP, D-dimers, troponin
 - 2.1.3 Radiologic studies: CT chest without IV contrast preferably prior to treatment with methylprednisolone.
 - 2.1.4 Other studies:
 - 2.1.4.1 Either PCR for molecular detection of SARS-Cov-2 virus and serologic rapid test (IgG, IgM), or both (see figure 2). Cases who are IgG positive but IgM negative, will not be considered eligible unless they are positive by molecular PCR test or they are acutely ill with symptoms typical of Covid-19 (see section 6.2 for typical symptoms).
 - 2.1.4.2 O₂ saturation by pulse oximetry
 - 2.1.4.3 Influenza rapid test if considered necessary.
- 2.2 During study (only applies to those eligible for treatment with methylprednisolone):
 - 2.2.1 For patients admitted to hospital: Vital signs q 8 hours (not q 4 hrs) to reduce chance of nursing staff contamination
 - 2.2.2 Day 7-10 from first symptom of illness: CBC, CMP, LDH, serum IL-6, serum ferritin, CRP, d-dimers
 - 2.2.3 Day 14 from registration on trial:

- 2.2.3.1 repeat CBC, CMP, LDH, serum IL-6, serum ferritin, CRP, d-dimers
- 2.2.3.2 repeat PCR for molecular detection of SARS-Cov-2 virus
- 2.2.4 Day 28 from registration on trial:
 - 2.2.4.1 repeat CBC, CMP, LDH, serum IL-6, serum ferritin, CRP, d-dimers
 - 2.2.4.2 repeat PCR for molecular detection of SARS-Cov-2 virus
 - 2.2.4.3 CT chest without IV contrast

[figure not shown]

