4.0 Study Objectives and End Points

Primary Objective:

- 1- To decrease the rate of progression to hypoxemic respiratory failure in high risk patients with Covid-19, treated with prophylactic steroids during the first phase of the disease.
 - a. Hypoxemic respiratory failure is defined as:
 - 1. O_2 saturation of < 91% or pO_2 <60 on room air
- 2- To evaluate the rate of complications of patients observed without treatment.
 Complications include progression to respiratory failure or any other complication leading to hospitalization.

Secondary Objectives:

- 1. To determine % survival at 28 days from registration on this clinical trial
- 2. To determine if there is any improvement in inflammatory markers following treatment with corticosteroids.
- 3. To define the length of hospitalization
- 4. To determine the frequency of admissions to ICU.
- 5. To determine the percentage of patients who require ventilatory support.
- 6. To determine the rate of complications and progression to respiratory failure in patients with favorable features (i.e., those eligible for observation and not for therapy with methylprednisolone.)
 - a. To validate these results in an independent cohort of cases diagnosed as Covid-19 from our general hospital population.
- 7. We will evaluate the proportion of patients with clinical improvement, as defined by live discharge from the hospital, a decrease of at least 2 points from baseline on a modified ordinal scale (as recommended by the WHO R&D Blueprint Group), or both. [10]
 - 7.1 The six-point scale consists of the following categories:
 - (1) not hospitalized;

- (2) hospitalized, not requiring supplemental oxygen;
- (3) hospitalized, requiring supplemental oxygen;
- (4) hospitalized, requiring nasal high-flow oxygen therapy, noninvasive mechanical ventilation, or both;
- (5) hospitalized, requiring invasive mechanical ventilation, ECMO, or both; and
- (6) death.

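### The complication rate in untreated patients (primary objective 2, secondary objective 6) cannot be answered from the data the protocol requires

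*Protocol*

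**What the plan says.** Protocol section 4.0 makes this a primary objective: "To evaluate the rate of complications of patients observed without treatment". It defines the events: "Complications include progression to respiratory failure or any other complication leading to hospitalization". No time horizon is given. Secondary objective 6 asks for complications and respiratory failure in patients with favorable features, meaning those assigned to observation.

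On data collection in these patients, section 6.1 states: "Those who do not meet the criteria will only be registered with no need to collect further data except baseline labs and CT chest". The next sentence adds: "They should sign the consent form and the data manager can collect the rest of the information".

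The on-study part of the schedule, section 2.2, opens with a restriction: "During study (only applies to those eligible for treatment with methylprednisolone". The day 7-10, day 14 and day 28 items all sit below it. Item 2.2.2 reads: "Day 7-10 from first symptom of illness: CBC, CMP, LDH, serum IL-6, serum ferritin, CRP, d-dimers".

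On timing, section 6.3 says: "Eligible patients will be registered on study on or before 10 days from first onset of symptoms". Section 6.4 asks for at least two high-risk criteria "on or shortly before day 10 (but not before day 7" of illness. It adds that a patient who meets two criteria earlier is eligible, with treatment held until day 7.

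**The concern.** Both objectives count events that happen after registration. The protocol schedules no observation after baseline in the group where those events are to be counted. Study-hospital records would show some admissions, but they would miss patients who worsen at home or are admitted elsewhere. Those are the events that matter most here, because section 3.0 wants the data to guide which patients can be managed safely as outpatients.

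A secondary problem concerns who is in the observed group. Section 3.0 places the inflammatory phase about 7 to 10 days after onset and says that rising markers herald it. A patient registered before day 7 with fewer than two criteria has no scheduled day 7-10 panel, because that panel belongs to patients already eligible for treatment. The observed group may therefore include patients who later turned high risk. They would blur the low-risk rate and be lost from the population for primary objective 1.

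**Working it through.** The protocol gives no sample size, precision or power figure for the observed group, so there is nothing of its own to reproduce. The check sets the sections side by side and then sizes the gap.

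**What is needed and what is required**

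| Need | Source | Required in observed patients? |
|---|---|---|
| Respiratory failure after registration | 4.0, primary objective 2 and secondary objective 6 | No (2.2, 6.1) |
| Complication leading to hospitalization | 4.0, primary objective 2 | No (2.2, 6.1) |
| Time horizon for these events | Not stated for primary objective 2 | No |
| Markers at illness day 7-10 | 6.4 | No (2.2.2 covers treatment-eligible patients only) |
| Baseline labs and CT chest | 6.1 | Yes |

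**Size of the observed group.** Section 5.2 gives the total as 100 and 200 with the separator lost in the text at hand; I read it as a range. It expects at least 40 to 60 treated.

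- Smallest: 100 - 60 = 40.
- Largest: 200 - 40 = 160.

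Because the treated number is a minimum, 40 is not a floor; more than 60 treated would leave fewer observed. Total minus treated may also include untreated patients who are not low risk, since 6.1 registers all severities.

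**Precision if everyone were followed.** For zero events in n patients, the two-sided exact 95% upper limit is 1 - 0.025^(1/n).

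- n = 40: 1 - 0.025^(1/40) = 8.8%.
- n = 160: 1 - 0.025^(1/160) = 2.3%.

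With an assumed rate of 5%, the exact (Clopper-Pearson) 95% intervals are 0.6 to 16.9% (2/40) and 2.2 to 9.6% (8/160). The objective is estimable once outcomes are collected.

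**Bounds when outcomes are unknown.** With x known events and u unknown outcomes among n patients, the rate lies between x/n and (x + u)/n. As written, no outcome is required, so u = n and x = 0, and the bounds are 0 to 100% at any n.

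The next table assumes that informal collection reaches some patients and that about 5% of those reached have an event. Neither figure is in the protocol.

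| Share unknown | n = 40 | n = 160 |
|---|---|---|
| 10% | 2/40 to (2+4)/40: 5.0 to 15.0% | 7/160 to (7+16)/160: 4.4 to 14.4% |
| 25% | 2/40 to (2+10)/40: 5.0 to 30.0% | 6/160 to (6+40)/160: 3.8 to 28.8% |
| 50% | 1/40 to (1+20)/40: 2.5 to 52.5% | 4/160 to (4+80)/160: 2.5 to 52.5% |

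The width of these bounds equals the unknown share. At n = 160, 10% unknown (10 points) already exceeds the width of the sampling interval at 5% (9.6 - 2.2 = 7.4 points). At n = 40 the sampling interval is 16.9 - 0.6 = 16.3 points wide, so 10% unknown does not exceed it but 25% does.

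**The case against.** The strongest reply is that section 6.1 does not stop at baseline. It lets the data manager gather the remaining information, and section 3.0 has in mind some low-risk patients who are already in hospital, so some events would be in the chart. This stands in part. A reader might infer that the objective cannot be answered at all, or that nothing beyond baseline could ever be collected; the protocol does not go that far. But the sentence is permissive, follows one saying that no further data are needed, and names no variable, time point, contact or source. It leaves the objective without required data.

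Four other inferences go further than the text.

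- **28-day survival.** Secondary objective 1 names no population, and the day 28 items in 2.2.4 and 10.0.1 concern treated or treatment-eligible patients. Only primary objective 2 and secondary objective 6 clearly need outcomes in the observed group.
- **Circular classification.** Labs before day 7 can qualify a patient under 6.4, and nothing forbids a re-test or makes an early negative final. What holds is that no re-test is scheduled for early registrants below two criteria.
- **Missing events read as safety.** Section 12.1 asks for clinical data on at least one subsequent day, so on its face a patient with no follow-up is non-evaluable, not event-free. The rule is weak, since one day is enough and the section focuses on treated patients.
- **A matter for the SAP.** Analysis detail can wait for that document. Whom to follow, when and for which outcomes is a protocol matter, and no analysis plan can recover outcomes that were not collected.

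**Conclusion.** The concern holds in this form: primary objective 2 and secondary objective 6 cannot be answered from the data the protocol requires. This is a conflict between section 4.0 on one side and sections 2.2 and 6.1 on the other, not a missing detail. It leaves roughly 40 to 160 observed patients without a required outcome, on the reading of section 5.2 above. The attainable upper limit of 8.8% or 2.3% after zero events gives way to worst-case bounds of 0 to 100%. The 0 to 100% describes what the protocol guarantees; informal collection could narrow it by an amount that cannot be known in advance.

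The unscheduled re-test is a real but secondary point. The protocol gives no figure for how many patients would register before day 7 or convert later, so its size cannot be stated.

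**What to change.** - **Section 6.1:** replace the waiver of further data with a required outcome contact for every registered patient at day 28 from registration; a day 14 contact is optional. Both time points are already in section 2.2. Make the contact by telephone and supplement it with chart review; a chart alone would leave the gap at other hospitals and at home. Record respiratory failure, hospitalization at any hospital, ventilation and vital status.
- **Section 2.2:** state that this contact applies to all registered patients, whatever their eligibility for treatment.
- **Primary objective 2:** give it the same day 28 horizon, and count patients who cannot be reached as unknown, not as event-free.
- **Sections 2.2.2 and 6.4:** reconcile who has labs at illness day 7-10 with when the criteria are judged. The sponsor must settle this; I do not propose extending the panel, which would add a procedure and change who qualifies for treatment.
- **Reporting:** show observed patients classified only on labs before day 7 separately from those classified on day 7-10 labs.

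The cost is one or two short contacts per observed patient, so about 40 to 160 contacts at day 28 and up to twice that (80 to 320) if day 14 is added, plus the protocol wording.

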1.0 Study synopsis

This is a Phase II pilot exploratory study designed to investigate if prophylactic treatment with short term steroids administered to high risk Covid-19 patients might prevent cytokine storm and progression to respiratory failure. It is also designed to determine if it is feasible to identify a subset of cases with low risk for complications that can be observed as outpatients without treatment. High risk is defined based on serologic markers of inflammation that include abnormalities of IL-6, ferritin, D-dimer, LDH, as well as lymphopenia and impaired O_2 saturation prior to or on the 7^{th} - 10^{th} day of first symptom of Covid-19.

1.1 This is a non-randomized study which will be carried out at Auxilio Mutuo and possibly at other institutions to be recruited.

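### Patients first tested after day 10 cannot meet the treatment criteria in 6.4, and secondary objective 6 then counts them as having favorable features whatever their markers show

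*Protocol*

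**What the plan says.** **Registration.** Protocol 6.1 states that all diagnosed patients "will be registered on the study regardless of their severity", with steroids reserved for those at high risk. 6.3 sets registration at no later than 10 days from onset, then adds: "Patients whose symptoms started > 10 days ago; but who are not in respiratory failure are eligible if they are still symptomatic".

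**Treatment.** 6.4 asks for at least two of eight criteria, met "on or shortly before day 10 (but not before day 7"). Items 6.4.1 to 6.4.7 each repeat a limit of their own, for example "D-dimer > 1 mg/L (1,000 ng/ml) before day 10". Only 6.4.8, "CT chest with evidence of infiltrate(s"), has no day attached.

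**Everyone else.** For patients who are not treated, 6.1 says: "Those who do not meet the criteria will only be registered with no need to collect further data except baseline labs and CT chest". Section 4.0 makes the complication rate of untreated patients primary objective 2. Secondary objective 6 asks for the same kind of rate in patients with favorable features, and its parenthesis equates these with patients who are for observation and not for methylprednisolone.

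**Day 10 elsewhere.** The synopsis defines high risk by abnormalities "prior to or on the 7^{th} - 10^{th} day of first symptom of Covid-19". Item 2.2.2 lists "Day 7-10 from first symptom of illness: CBC, CMP, LDH, serum IL-6, serum ferritin, CRP, d-dimers", although section 2.2 applies only to patients already eligible for treatment.

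**The concern.** Section 3.0 says that the low-risk subset is to be found from inflammation markers together with other prognostic variables, and that the data should help decide who can be managed as an outpatient or discharged. The group that delivers this answer is defined by what is left over after 6.4. For a patient first tested after day 10, 6.4 gives the same answer whether the markers are normal or grossly abnormal. Two patients with identical results can therefore land in different groups because one was tested earlier.

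If this group is reported as written, the favorable-features rate describes a mixture: patients whose markers were examined in time and found acceptable, and patients whose markers could not count. The same patients sit unmarked in the observed group of primary objective 2.

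The day-10 wording is a smaller, separate defect. A site that draws blood on day 10 itself gets opposite answers from the stem and from the items.

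**Working it through.** **1. Count the criteria (6.4).**
- Items limited to before day 10: 6.4.1 to 6.4.7, which is 7 of 8.
- Items with no day of their own: 6.4.8 (CT), which is 1 of 8.
- Needed for treatment: 2.

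| First test | Most criteria that can count, by item wording | If the stem's window also governs CT |
|---|---|---|
| Before day 10 | 8 | 8 |
| On day 10 | 1 (CT) | 1 (CT; the stem includes day 10) |
| After day 10 | 1 (CT) | 0 |

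After day 10 the maximum is 1 or 0, below the 2 required, so no marker value can qualify the patient. On day 10, the stem alone would allow all 8, while the items allow 1.

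**2. Who is affected.** Section 2.1 accepts tests done at or before entry. A patient who registers late but has two qualifying earlier values can still be treated. A late registrant tested in time with fewer than two criteria is properly classified. Only patients first tested after day 10 are sorted by date.

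**3. Where they go.** Not meeting 6.4 means registered and untreated (6.1). Untreated means counted in primary objective 2. Not eligible for methylprednisolone means favorable features, by the parenthesis in secondary objective 6. No other definition of favorable features is given.

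**4. Possible size (illustration; every rate and share is assumed).** The Protocol gives neither the share of late-tested patients nor their complication rate. Let s be their share of the group, h their complication rate, and 5% the rate in the rest:

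observed rate = (1 - s) × 0.05 + s × h, so the shift is s × (h - 0.05).

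| h | s = 5% | s = 10% | s = 20% | Largest shift |
|---|---|---|---|---|
| 2% | 4.85% | 4.7% | 4.4% | 0.20 × (-0.03) = -0.6 points |
| 5% | 5.0% | 5.0% | 5.0% | 0 |
| 25% | 6.0% | 7.0% | 9.0% | 0.20 × 0.20 = +4.0 points |
| 50% | 7.25% | 9.5% | 14.0% | 0.20 × 0.45 = +9.0 points |

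The last row borrows the untreated risk of more than 50% that 5.3 assumes for patients meeting the entry criteria; 5.3 does not say it applies to late patients. The sign depends on h. Late patients with high markers may be at greater risk, but patients past day 10 without respiratory failure may have come through part of the risk period.

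**The case against.** **No contradiction between 6.3 and 6.4.** 6.3 decides who is registered and 6.4 decides who is treated, and both can be followed literally. A treatment window closing at about day 10 also fits the rationale: primary objective 1 concerns steroids in the first phase of the disease, section 3.0 ends that phase 7 to 10 days after onset, and it attributes the unfavorable steroid data partly to late use. This objection stands.

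**A stronger reading that a reader might infer** is that 6.3 was meant to open treatment to late patients and that 6.4 blocks it. 6.1 already registers everyone, so the condition about respiratory failure seems to add little for registration alone. And 8.3 dates dosing from registration: with registration on illness day 11 counted as day 1, dosing would start on illness days 11 to 13. The documents do not support this. Respiratory failure is a counted complication under primary objective 2, so leaving out late patients who already have it makes sense for an observed group. 8.3 only schedules patients who have qualified.

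**The markers are not lost.** Section 2.1.2 measures them at entry, 6.1 retains baseline labs and CT, and 6.6 applies the CALL score to all cases. It would be wrong to say that these patients have no risk information. It is there, but the definition in secondary objective 6 does not use it.

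**Subgroup reporting belongs in an analysis plan.** This is true of the extra reporting row in itself. It does not cover the definition of favorable features, which the Protocol fixes and which conflicts with its stated aim.

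**Conclusion.** The concern holds in a limited form. As written, 6.4 cannot classify a patient first tested after day 10 by risk, and secondary objective 6 then labels that patient favorable. This contaminates the favorable-features rate and mixes such patients into the observed group of primary objective 2. It matters because section 3.0 wants these data to guide outpatient care and discharge.

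The size is not determinable from the Protocol. The illustrative shifts of -0.6 to +9.0 points rest on assumed shares and rates and change sign, so a reader should not infer that the observed rate is necessarily inflated. The conclusion assumes that the parenthesis in secondary objective 6 is applied literally and that some late registrants have no earlier tests.

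The day-10 mismatch between the stem and synopsis on one side and seven items on the other is a plain inconsistency that depends on none of this. Both should be corrected; neither invalidates the treatment rule.

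**What to change.** 1. In 6.4.1 to 6.4.7, change the limit to on or before day 10, to match the stem and the synopsis.
2. State in 6.3 or 6.4 that patients who do not have two criteria met by day 10, CT included, are registered for observation only.
3. In secondary objective 6, define favorable features as fewer than two 6.4 criteria among patients whose values were obtained by day 10. Report patients first tested after day 10 as a separate observed group, described by baseline labs and CALL score.
4. If any late-tested patient is treated all the same, keep that patient evaluable, since 12.0 counts everyone given at least one dose, and report the 5.4 proportion with and without such patients. If the 40 to 60 eligible patients in 5.2 are reached and treated, each weighs at most 1/40 = 2.5 points, or 1/60 = 1.7 points.

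The cost is a wording amendment, one extra reporting row and a slightly smaller favorable-features group. No new data are needed: onset date, baseline labs and CT are already required by 6.1, 6.3 and 6.4.

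### A saturation of exactly 91% is neither a high-risk criterion (6.4.7) nor respiratory failure (4.0), so a patient at 91% can go untreated where the same patient at 92–93% is treated

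*Protocol*

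**What the plan says.** Section 6.1 of the protocol states that all patients diagnosed with Covid-19 "will be registered on the study regardless of their severity", and that only those who meet the high-risk criteria receive steroids. Section 6.4 sets the treatment rule. It begins "In order to be treated with methylprednisolone, they must meet at" and goes on to require two or more of the eight items 6.4.1 to 6.4.8. Item 6.4.7 is a saturation below 94% "by pulse oximetry, but more than 91%, before day 10".

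Section 4.0, under the first primary objective, defines hypoxemic respiratory failure as "saturation of < 91% or pO_2 <60 on room air".

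Three other provisions bear on a patient who is not treated:

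- The assessments in section 2.2 are headed as one that "only applies to those eligible for treatment with methylprednisolone".
- Section 6.1 says that for untreated patients "the data manager can collect the rest of the information".
- The second primary objective is "To evaluate the rate of complications of patients observed without treatment".

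**The concern.** The lower limit in 6.4.7 has a clear purpose. It separates patients at risk of respiratory failure from those who already have it. For that to work, the criterion must start where the failure definition stops. Here one limit is strictly above 91% and the other strictly below it, so 91% itself falls between them.

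The result runs against the aim of the trial. Of two patients who have not failed and who each have one other criterion, the one with the lower saturation does not get the study drug. That patient joins the observed group, which secondary objective 6 describes as having favorable features, and does not have the scheduled laboratory tests, PCR and CT of section 2.2. The protocol hopes to use that group to identify patients who can be managed safely outside hospital, so a patient one point from the failure limit does not belong there.

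**Working it through.** No sample size, power or error rate is involved. The check is of the logic of the cut-offs.

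**Inputs**

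- Saturation criterion (6.4.7): met if 91 < sat < 94.
- Failure by saturation (4.0): sat < 91. Failure by blood gas: pO2 < 60 on room air. Blood gases are scheduled at entry (section 2.1.2 lists "arterial blood gases, serum IL-6" among the laboratory tests), so the check is restricted to patients with pO2 of at least 60.
- Treatment rule (6.4): at least two of eight criteria. With k the number of the other seven criteria met (0 to 7), a patient is treated if k + I(91 < sat < 94) ≥ 2, where I is 1 if the condition holds and 0 otherwise.
- Assumptions: saturation is read in whole percent, and the patient has no 92–93% reading in the qualifying window.

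**Step 1: one other criterion met (k = 1)**

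| Saturation | 6.4.7 met | Failure by saturation | Criteria met | Treated |
|---|---|---|---|---|
| 88–90% | no | yes | 1 | no |
| 91% | no | no | 1 | no |
| 92–93% | yes | no | 2 | yes |
| 94–96% | no | no | 1 | no |

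The only whole-percent value below 94% outside both rules is 91%.

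**Step 2: other values of k**

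At k = 0 the total is at most 1, so nobody is treated at any saturation. At k ≥ 2 everyone is treated at any saturation. The gap therefore acts only at k = 1.

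**Step 3: effect of closing the gap**

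Replace the condition with 91 ≤ sat < 94. The readings that count go from {92, 93} to {91, 92, 93}. Over saturations 80 to 100% and k from 0 to 7 there are 21 × 8 = 168 combinations. Treatment changes in one of them, sat = 91 with k = 1, where the total goes from 1 + 0 = 1 to 1 + 1 = 2. This counts rule combinations and is not a share of patients.

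**Step 4: order reversals among patients not in failure**

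Within 91–93%, count the pairs with equal k in which the lower saturation is untreated and the higher is treated. As written there are two, 91 against 92 and 91 against 93, both at k = 1. With the change there are none. Reversals that involve 90% or below remain under both rules, but those patients already meet the failure definition.

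**The case against.** The strongest reply is that the gap is real but immaterial. A patient must read exactly 91%, have pO2 of at least 60, meet exactly one of seven other criteria, and have no 92–93% reading in the window. Several of those criteria are easy to meet (IL-6 of 10 pg/ml or more, any LDH above normal, any infiltrate on CT). On the protocol's own account of the disease, inflammatory markers and infiltrates appear together, so many patients at 91% would qualify anyway. This stands, and it is why the point is minor.

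Three further arguments carry less weight:

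- **Intent.** The synopsis lists impaired saturation as a high-risk marker without a lower limit, so a site query about 91% might be answered sensibly. That does not override the explicit limit in 6.4.7.
- **Follow-up.** Missing the section 2.2 tests is the lot of every observed patient by design. That is right; the gap only determines that this patient is one of them. Nor is the outcome shown to be lost, given the data collection allowed in 6.1 and the second primary objective.
- **A larger issue nearby.** A patient below 91% with two other criteria can still qualify under 6.4 while already meeting the failure definition. That is a separate matter. It neither rebuts this point nor is solved by the change proposed here.

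**Conclusion.** The point holds as a minor error. As written, 6.4.7 and 4.0 both leave out a saturation of exactly 91%. Among patients not in failure, this withholds treatment from one at 91% with a single other criterion while giving it to the same patient at 92% or 93%.

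The conclusion about the wording is firm, because both inequalities are explicit. The practical size is small and cannot be quantified, since the protocol gives no distribution of saturations or of criteria met. The description of the gap as one of three readings rests on whole-percent oximetry; with decimal readings, only 91.0% itself would be left out. No change in the failure rate of treated patients, the complication rate of observed patients, or the verdict under 5.4 has been shown. The lower limit as such is not disputed for patients below 91%, who already meet the failure definition.

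**What to change.** Reword 6.4.7 so that the criterion is a saturation below 94% and at least 91%. Leave the failure definition in 4.0 as it is. The two saturation limits then meet at 91%, and a patient at 91% who is not in failure is handled like one at 92–93%.

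Moving the failure limit to 91% or below would also close the gap, but it would alter the primary endpoint, so the change belongs in 6.4.7.

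The cost is one inequality. The endpoint, success rule, sample size and assessment schedule do not change.
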